### **6.1.1      *Serious Adverse Event Collection and Reporting***

Sections 5.5.1 in the Investigator Brochure (IB) represent the Reference Safety Information to determine expectedness of serious adverse events for expedited reporting. Following the subject's written consent to participate in the study, all SAEs, whether related or not related to study drug, must be collected, including those thought to be associated with protocol-specified procedures. All SAEs must be collected that occur during the screening period and within 85 days of discontinuation of the Treatment Period. If applicable, SAEs must be collected that relate to any later protocol-specified procedure (eg, a follow-up skin biopsy).

The investigator must report any SAE that occurs after these time periods and that is believed to be related to study drug or protocol-specified procedure.

An SAE report must be completed for any event where doubt exists regarding its seriousness.

If the investigator believes that an SAE is not related to study drug, but is potentially related to the conditions of the study (such as withdrawal of previous therapy or a complication of a study procedure), the relationship must be specified in the narrative section of the SAE Report Form.

SAEs, whether related or not related to study drug, and pregnancies must be reported to BMS (or designee) within 24 hours of awareness of the event. SAEs must be recorded on the SAE Report Form; pregnancies on a Pregnancy Surveillance Form (electronic or paper forms). The preferred method for SAE data reporting collection is through the eCRF. The paper SAE/pregnancy surveillance forms are only intended as a back-up option when the eCRF system is not functioning. In this case, the paper forms are to be transmitted via email or confirmed facsimile (fax) transmission to:

**SAE Email Address:** Refer to Contact Information list.

**SAE Facsimile Number:** Refer to Contact Information list.

For studies capturing SAEs through electronic data capture (EDC), electronic submission is the required method for reporting. In the event the electronic system is unavailable for transmission, paper forms must be used and submitted immediately. When paper forms are used, the original paper forms are to remain on site.

**SAE Telephone Contact** (required for SAE and pregnancy reporting): Refer to Contact Information list.

If only limited information is initially available, follow-up reports are required. (Note: Follow-up SAE reports must include the same investigator term(s) initially reported.)

If an ongoing SAE changes in its intensity or relationship to study drug or if new information becomes available, the SAE report must be updated and submitted within 24 hours to BMS (or designee) using the same procedure used for transmitting the initial SAE report.

All SAEs must be followed to resolution or stabilization.

## **6.2 Nonserious Adverse Events**

A *nonserious adverse event* is an AE not classified as serious.

### **6.2.1 Nonserious Adverse Event Collection and Reporting**

The collection of nonserious AE information should begin at initiation of study drug. Nonserious AE information should also be collected from the start of a placebo lead-in period or other observational period intended to establish a baseline status for the subjects.

Nonserious AEs should be followed to resolution or stabilization, or reported as SAEs if they become serious (see [Section 6.1.1](#)). Follow-up is also required for nonserious AEs that cause interruption or discontinuation of study drug and for those present at the end of study treatment

as appropriate. All identified nonserious AEs must be recorded and described on the nonserious AE page of the CRF (paper or electronic).

Completion of supplemental CRFs may be requested for AEs and/or laboratory abnormalities that are reported/identified during the course of the study.

### **6.3        Laboratory Test Result Abnormalities**

The following laboratory test result abnormalities should be captured on the nonserious AE CRF page or SAE Report Form (paper or electronic) as appropriate:

- Any laboratory test result that is clinically significant or meets the definition of an SAE
- Any laboratory test result abnormality that required the subject to have study drug discontinued or interrupted
- Any laboratory test result abnormality that required the subject to receive specific corrective therapy

It is expected that wherever possible, the clinical rather than laboratory term would be used by the reporting investigator (eg, anemia versus low hemoglobin value).

### **6.4        Pregnancy**

If, following initiation of the study drug, it is subsequently discovered that a study subject is pregnant or may have been pregnant at the time of study exposure, including during at least 5 half lives after product administration, the investigator must immediately notify the BMS Medical Monitor/designee of this event and complete and forward a Pregnancy Surveillance Form to BMS Designee within 24 hours of awareness of the event and in accordance with SAE reporting procedures described in [Section 6.1.1](#).

In most cases, the study drug will be permanently discontinued in an appropriate manner (eg, dose tapering if necessary for subject safety).

In the rare event that the benefit of continuing study drug is thought to outweigh the risk, after consultation with BMS, the pregnant subject may continue study drug after a thorough discussion of benefits and risk with the subject.

Protocol-required procedures for study discontinuation and follow-up must be performed on the subject unless contraindicated by pregnancy (eg, x-ray studies). Other appropriate pregnancy follow-up procedures should be considered if indicated.

The investigator must immediately notify the BMS (or designee) Medical Monitor of this event and complete and forward a Pregnancy Surveillance Form to BMS (or designee) within 24 hours of awareness of the event and in accordance with SAE reporting procedures described in [Section 6.1.1](#).

Follow-up information regarding the course of the pregnancy, including perinatal and neonatal outcome and, where applicable, offspring information must be reported on the Pregnancy Surveillance Form.

Any pregnancy that occurs in a female partner of a male study participant should be reported to BMS. Information on this pregnancy will be collected on the Pregnancy Surveillance Form.

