### **3.5 Discontinuation of Subjects following any Treatment with Study Drug**

Subjects MUST discontinue investigational product (and non-investigational product at the discretion of the investigator) for any of the following reasons:

- Use of prohibited medication
- Pregnancy
- Missed Doses:
  - Missed greater than 6 doses of abatacept OR greater than 3 doses of adalimumab for any reason during the study
  - Missed greater than 4 consecutive doses of abatacept OR greater than 2 consecutive doses of adalimumab for any reason during the study
- Any clinical adverse event (AE), laboratory abnormality or intercurrent illness which, in the opinion of the investigator, indicates that continued participation in the study is not in the best interest of the subject.
- Subject's request to stop study treatment or withdrawal of informed consent
- Termination of the study by Bristol-Myers Squibb (BMS)
- Loss of ability to freely provide consent through imprisonment or involuntarily incarceration for treatment of either a psychiatric or physical (eg, infectious disease) illness

All subjects who discontinue study drug should comply with protocol specified follow-up procedures as outlined in [Section 5](#). The only exception to this requirement is when a subject withdraws consent for all study procedures including post-treatment study follow-up or loses the ability to consent freely (ie, is imprisoned or involuntarily incarcerated for the treatment of either a psychiatric or physical illness).

If study drug is discontinued prior to the subject's completion of the study, the reason for the discontinuation must be documented in the subject's medical records and entered on the appropriate case report form (CRF) page.

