## **4              STUDY DRUG**

Study drug includes both Investigational [Medicinal] Product (IP/IMP) and Non-investigational [Medicinal] Product (Non-IP/Non-IMP).

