## **4.2 Non-investigational Product**

In this protocol, non-investigational product(s) include include methotrexate, corticosteroids, NSAIDs, (including aspirin), folic acid, and/or folinic acid (leucovorin). BMS will not provide non-investigational products.

Other medications used as support or escape medication for preventative, diagnostic, or therapeutic reasons, as components of the standard of care for a given diagnosis, may be considered as non-investigational products.

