#### **4.5.3    *Guidelines for Methotrexate***

Subjects must enroll on a stable minimum targeted dose of 20 mg/week. Subjects may enroll with MTX doses  $< 20$  mg/week but  $\geq 7.5$  mg/week if intolerance to higher doses has been recorded in the source documents. All subjects must be maintained on the enrollment MTX dose, unless toxicity or intolerance occurs during the course of the study. In that event, the dose may be reduced or held as medically necessary for adverse events. However, MTX should be returned to the baseline dose as soon as possible, or to the maximally tolerated dose below the baseline dose, but not less than 7.5 mg/week for the duration of the study. MTX should be given orally.

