### **5.3.6.5 *Pregnancy Tests***

Urine/serum pregnancy tests (minimum sensitivity 25 IU/L of  $\beta$ -HCG) must be performed for all WOCBP within 24 hours prior to dosing for visits specified in [Section 5.1](#). A serum test must be performed for confirmation of any positive urine test result. Urine tests can be processed locally and can be self-administered by the subject between office visits, if permitted by local regulations. If any female subject becomes pregnant, she will stop receiving study treatment immediately and enter the Post Treatment Follow-up Period. A pregnancy surveillance form will be completed and submitted to Bristol-Myers Squibb. Serum pregnancy tests will be processed centrally.

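### Section 6.4 of the protocol allows a pregnant subject to continue study drug, which by definition includes abatacept and adalimumab, although Sections 3.5 and 5.3.6.5 require a stop

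*Protocol*

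**What the plan says.** Four places in the original protocol bear on a subject found to be pregnant during treatment.

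- **Section 3.5 (discontinuation).** "Subjects MUST discontinue investigational product (and non-investigational product at the discretion of the investigator) for any of the following reasons". Pregnancy is on the list that follows, with no qualification.
- **Section 5.3.6.5 (pregnancy tests).** "If any female subject becomes pregnant, she will stop receiving study treatment immediately and enter the Post Treatment Follow-up Period".
- **Section 6.4 (pregnancy).** The default is a stop, but not in every case: "In most cases, the study drug will be permanently discontinued in an appropriate manner (eg, dose tapering if necessary for subject safety"). An exception follows for rare cases where continuing is judged to do more good than harm. Once the sponsor has been consulted, "the pregnant subject may continue study drug after a thorough discussion of benefits and risk with the subject". The same section requires immediate notification of the medical monitor and a surveillance form within 24 hours.
- **Section 4 (definition).** "Study drug includes both Investigational [Medicinal] Product (IP/IMP) and Non-investigational [Medicinal] Product (Non-IP/Non-IMP"). Section 4.1 names abatacept and adalimumab as the investigational products. Section 4.2 lists methotrexate, corticosteroids, NSAIDs and folic or folinic acid as non-investigational.

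**The concern.** Whether a pregnant subject goes on receiving a randomized biologic is a subject-level safety rule, and a site needs one answer on the day a test is positive. Section 3.5 forbids continuation of investigational product. Section 6.4 describes it as available under conditions. The rest of the protocol is built to avoid exposure in pregnancy: a negative test within 24 hours before the first dose, contraception during treatment and for 100 days after it (Section 3.3.1), and repeated testing during treatment (Table 5.1-2). An exception that reaches the two randomized drugs is out of line with that intent. What is at stake is subject safety and consistent conduct, not any estimate or test.

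**Working it through.** No arithmetic applies, so the check is a comparison of the texts.

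**Step 1: what 'study drug' means in 6.4.** Section 6.4 uses the term without narrowing it. Section 4 defines it as investigational plus non-investigational product. Abatacept and adalimumab are investigational product (Section 4.1), so the exception in 6.4 covers them.

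**Step 2: the rules side by side, for abatacept and adalimumab in a known pregnancy.**

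| Section | Term used | Rule | Exception |
|---|---|---|---|
| 3.5 | investigational product | must stop | none |
| 5.3.6.5 | study treatment | stop at once, enter follow-up | none |
| 6.4 | study drug | stop in most cases | may continue if benefit is thought to outweigh risk, after sponsor consultation and discussion with the subject |

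'Study treatment' is not defined in Section 4. Whatever else it covers, it must cover the randomized injections, so 5.3.6.5 sides with 3.5.

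**Step 3: can all three be followed?** If the subject stops, yes. If continuation under the 6.4 exception is proposed, no: using it breaches 3.5 and 5.3.6.5.

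**Step 4: is there a rule of precedence?** None is visible. Section 6.4 does not refer to 3.5, and 3.5 does not refer to 6.4. Reading the specific text over the general one does not settle it: 6.4 is the more specific section on pregnancy, while 3.5 is the more specific on which product must stop.

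**Step 5: does any analysis depend on it?** No. The protocol and SAP define no primary or secondary endpoint. The as-treated population is fixed by receipt of at least one dose, so stopping or continuing later does not change membership. No visible SAP rule refers to pregnancy.

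**The case against.** **The 6.4 exception is meant for background drugs only.** This is the most charitable reading, and the tapering example gives it some support: both randomized drugs come as fixed-dose prefilled syringes, so tapering fits them poorly. But the section does not say so, and the definition in Section 4 says otherwise.

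**The safeguards make it harmless.** Two sections already require a stop. Section 6.4 itself requires medical monitor notification, sponsor consultation and the study's discontinuation and follow-up procedures, and Section 6.1 has pregnancy handled as a serious adverse event. No site could properly use the exception on its own. This stands, and it is why the point is a small one. It does not remove the contradiction, because the sponsor consultation is itself the route by which 6.4 would allow what 3.5 forbids.

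**Stronger readings that the documents do not support.**

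- *A second contradiction, on methotrexate.* A reader might infer one because 3.5 leaves non-investigational product to the investigator, 6.4 sets a default stop with sponsor consultation, and Section 4.5.3 says "All subjects must be maintained on the enrollment MTX dose, unless toxicity or intolerance occurs during the course of the study". But an investigator can exercise the discretion in 3.5 while meeting the conditions in 6.4, so both can be followed. Section 4.5.3 also lets the dose be reduced or held for adverse events. Neither 3.5 nor 6.4 names methotrexate, so the difference arises only through the definitions. The published text also has a redacted block between Sections 3.3.3 and 3.5, so the lack of a visible methotrexate rule there proves nothing. A cross-reference is all that is needed.
- *A count of further doses at risk.* One could count the injections left in the schedule after a positive test. Such a count supposes that the sponsor approves continuation against 3.5 and that every later dose is taken. Nothing in the documents makes that a realistic course, so the count does not measure the problem.

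**Conclusion.** The contradiction on investigational product is real and follows from the visible wording of Sections 3.5, 4, 5.3.6.5 and 6.4. It should be corrected, but it is not urgent.

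Its size is small. The number of affected subjects is likely very low in a trial planned at 50 and later raised to 2 x 40 = 80 (SAP Section 5). That is an assumption, since no pregnancy rate is given. No endpoint, population or analysis changes.

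The conclusion applies to the original protocol only. The SAP (Section 2.4) describes Amendments 1, 2 and 6, whose full text is not supplied, and any of the later versions may have changed the wording.

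**What to change.** First check whether the current amended protocol still carries the conflict. If it does:

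1. **Section 6.4.** Add before the sentence on most cases: *Investigational product (abatacept or adalimumab) must be permanently discontinued, as required in Section 3.5.* State that the 'most cases' and 'rare event' sentences do not apply to investigational product.
2. **Section 6.4, background therapy.** If those two sentences are kept, limit them to methotrexate by name. Rewriting them for all non-investigational product would place a default stop on folic acid, folinic acid and corticosteroids, which nobody is likely to intend in a pregnant subject.
3. **Section 5.3.6.5.** Replace 'study treatment' with 'investigational product'. If the sponsor also wants methotrexate stopped at once, 6.4 should say so by name.
4. **Section 3.5.** Add to the pregnancy bullet a cross-reference to 6.4 for methotrexate.

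The cost is a wording change that needs IRB/IEC approval as an amendment (Section 9.1.1). The only option lost for the randomized drugs is one that 3.5 already forbids. Data collection, sample size and analysis stay as they are. SAP Section 7.7.1 indicates that the single-blind analysis had already been run when that version was written. If dosing has ended, the change is useful only for later protocols that reuse this text.

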## **6.5 Overdose**

An overdose is defined as the accidental or intentional administration of any dose of a product that is considered both excessive and medically important. All occurrences of overdose must be reported as an SAE (see [Section 6.1.1](#) for reporting details.).

## **6.6 Potential Drug Induced Liver Injury (DILI)**

Specific criteria for identifying potential DILI have not been identified for this protocol. Standard medical practice in identifying and monitoring hepatic issues should be followed.

## **6.7 Other Safety Considerations**

Any significant worsening noted during interim or final physical examinations, electrocardiogram, x-ray filming, any other potential safety assessment required or not required by protocol should also be recorded as a nonserious or serious AE, as appropriate, and reported accordingly.

# **7 DATA MONITORING COMMITTEE AND OTHER EXTERNAL COMMITTEES**

Not applicable

# **8 STATISTICAL CONSIDERATIONS**

## **8.1 Sample Size Determination**

In this study 25 subjects will be randomized per treatment arm.

This is an exploratory study with only exploratory objectives. No formal sample size and power calculation will be provided. It should be noted that with 25 subjects per arm the half width of the 95% CI for differences in proportion (eg, proportion of seroconversion for anti-CCP2, ACPA) will range from 25 to 30%. This means that only if the treatment difference in proportion is larger than 25-30% the difference will be declared statistically significant at 5% significance level. For changes from baseline in continuous variables the minimal detectable effect size (treatment difference in changes divided by common standard deviation) to declare statistical significance (with 5 % significance level) is 0.57.

The population will be enriched to allow for assessment of important changes in the immune phenotype by including only subjects who are anti-CCP2 positive.

## **8.2 Populations for Analyses**

The as-treated analysis population will contain all subjects who received at least 1 dose of study medication. The treatment that is received will be used in the analysis. This population will be used for all analyses, including demography, biomarker, efficacy and safety analyses.

[figure not shown]

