### **3.2 Post Study Access to Therapy**

At the end of the study, BMS will not continue to provide BMS supplied study drug to subjects/investigators unless BMS chooses to extend the study. The investigator should ensure that the subject receives appropriate standard of care to treat the condition under study.

Treatment codes will not be provided to the investigators after completion of the study as the study drug is provided in an open-labeled fashion to sites during the study.

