6.3 Populations for Analyses

The as-treated analysis population will contain all randomized subjects who received at least one dose of single-blind study medication, and subjects will be grouped on an as-randomized basis unless the subject received the incorrect medication for the entire period of single-blind treatment. In that case, the subject will be analyzed in the treatment group associated with the incorrect medication they received. This population will be used for all analyses of the single blind period, including demography, baseline disease characteristics, biomarker, efficacy safety and immunogenicity analyses and for the Week 48 efficacy and biomarker analyses.

The open-label abatacept population will contain all subjects treated with open-label abatacept.

The cumulative abatacept population will contain all subjects treated with single-blind and/or open-label abatacept.

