7 STATISTICAL ANALYSES

7.1 General Methods

All the analyses, with the exception of the analysis for efficacy responder rate, will be 'as-observed', ie. the available data will be used and there will be no imputation for missing values. For the efficacy responder rate analysis a non-responder imputation will be applied for missing data.

In [APPENDIX 1](#) the list of biomarkers is shown. The different biomarkers are classified into different biomarker categories (category 1 up to 12). The biomarker results (tables and plots) will be provided for each of these biomarker categories separately.

The focus of the exploration will be on Day 169 analysis. However, mean or median changes from baseline (with 95 % CI) over time from day 1 to day 169 of the single-blind period will be displayed for all biomarkers. These plots will be grouped by biomarker category (see [APPENDIX 1](#)).

All Day 337 analyses and analyses over time from day 1 to day 337 (efficacy and biomarkers) will be provided by original randomized treatment and grouped by biomarker category if applicable (see [APPENDIX 1](#)).

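### SAP 6.3 and 7.1 can place a subject who took the wrong drug throughout in different arms, and subjects randomized but never dosed leave the responder denominator

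*Protocol*

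**What the plan says.** Protocol 8.2 defines one population: "The as-treated analysis population will contain all subjects who received at least 1 dose of study medication". On grouping it says "The treatment that is received will be used in the analysis", and on scope "This population will be used for all analyses, including demography, biomarker, efficacy and safety analyses". The protocol supplied is dated 27-Jul-2015 and has a 24-week treatment period only.

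SAP 6.3 keeps the name and the one-dose condition: "The as-treated analysis population will contain all randomized subjects who received at least one dose of single-blind study medication". It changes the grouping: "subjects will be grouped on an as-randomized basis unless the subject received the incorrect medication for the entire period of single-blind treatment". In that exceptional case the subject goes to the arm of the drug taken. SAP 6.3 uses this population for all single-blind analyses and for Week 48 efficacy and biomarkers.

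SAP 7.1 states that Day 337 analyses, and efficacy and biomarker analyses over time from Day 1 to Day 337, "will be provided by original randomized treatment and grouped by biomarker category if applicable". It makes Day 169 the focus of the exploration. Responder rates use non-responder imputation, and everything else is as observed.

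On knowledge of allocation, Protocol 3.2 notes that "the study drug is provided in an open-labeled fashion to sites during the study". Protocol 4.6 accepts that subjects cannot be blinded; only the clinical assessor is.

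**The concern.** There are two separate issues.

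The first is consistency. For a subject who took the wrong drug for the whole single-blind period, SAP 6.3 points to the arm received and SAP 7.1 to the arm randomized. Both sections cover Week 48, which is Day 337 in SAP Table 8.5-2. The Day 1 to 337 displays also contain Day 169, so one Day 169 value could be summarized under one arm in the Week 24 output and under the other in the longitudinal output. Protocol 4.6 leaves the sponsor's statistician unblinded, and SAP 7.2 says relevant protocol deviations will not be assessed. An unresolved rule would therefore be settled by someone who can see allocation, and the reader might have no other sign that it had been applied.

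The second is exclusion after randomization. Site and subject know the drug once it is assigned. Someone who leaves at that point, before the first injection, disappears from the responder rate. Someone who takes one injection, leaves and has no Week 24 value stays in as a non-responder. If reluctance to start differs between the drugs, the two denominators are selected differently. The documents plan to declare differences significant at the 5% level (Protocol 8.1, SAP 5), and the randomized comparison is what supports that reading.

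**Working it through.** **1. The rules side by side**

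| Subject | Protocol 8.2 | SAP 6.3 (Week 24, Week 48) | SAP 7.1 (Day 337, Day 1 to 337) |
|---|---|---|---|
| Right drug throughout | randomized arm | randomized arm | randomized arm |
| Wrong drug for part of the single-blind period | by drug received | randomized arm | randomized arm |
| Wrong drug for the whole single-blind period | arm received | arm received | randomized arm |
| Randomized, never dosed | excluded | excluded | no population of its own, so excluded under 6.3 |

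Within the SAP, only the third row conflicts. The second row is a protocol-to-SAP difference. The fourth row is the same in both documents.

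**2. The plan's own precision, as a yardstick**

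The 95% half-width for a difference in proportions is 1.96 × √(2p(1−p)/n).

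- n = 40: p = 0.2 gives 17.5 points and p = 0.5 gives 21.9. SAP 5 states 17 to 21, so this is reproduced approximately.
- n = 25: p = 0.3 gives 25.4 and p = 0.5 gives 27.7. Both documents state 25 to 30, again approximate.
- At p = 0.4: 1.96 × √(2 × 0.4 × 0.6/40) = 21.5 points for n = 40, and 27.2 for n = 25.

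**3. Size of the effect per subject**

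The arm sizes of 25 and 40 are from SAP 5. The 40% response rate in both arms is an assumption, giving r = 10 of 25 or r = 16 of 40. The numbers of undosed and wrong-drug subjects are not in the documents, so results are per subject.

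Moving one responder to the other arm shifts the difference by (r+1)/(n+1) − (r−1)/(n−1):

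- n = 40: 17/41 − 15/39 = 3.0 points
- n = 25: 11/26 − 9/24 = 4.8 points

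Moving one non-responder shifts it by r/(n+1) − r/(n−1):

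- n = 40: 16/41 − 16/39 = −2.0 points
- n = 25: 10/26 − 10/24 = −3.2 points

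Dropping k undosed subjects from one arm instead of counting them as non-responders raises that arm's rate by r/(n−k) − r/n:

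| k | n = 40 | n = 25 |
|---|---|---|
| 1 | 16/39 − 16/40 = 1.0 points | 10/24 − 10/25 = 1.7 points |
| 2 | 16/38 − 16/40 = 2.1 points | 10/23 − 10/25 = 3.5 points |
| 3 | 16/37 − 16/40 = 3.2 points | 10/22 − 10/25 = 5.5 points |

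Against the 21.5-point half-width at 40 per arm, one regrouped responder is 3.0/21.5, about 14%, and one undosed subject is 1.0/21.5, about 5%. If there are no such subjects, every entry is zero.

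**The case against.** A reader who starts from Protocol 8.2 might infer that the efficacy and biomarker comparisons are made by drug received throughout, so that randomization is abandoned. The documents do not support that. SAP 6.3 is later and more detailed, and it groups as randomized for everyone except a subject on the wrong drug for the entire single-blind period. SAP 2.4 cites Amendments 1, 2 and 6, while the protocol supplied predates them and has no Day 337 visit. Its as-received rule may simply have been superseded.

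The conflict between SAP 6.3 and 7.1 can also be read away. In 7.1 the reference to original randomized treatment may only separate the starting arms from the open-label abatacept that follows, and SAP 7.4.1 uses a similar phrase for open-label exposure. On that reading 6.3 governs and no value changes arm. That is possible, but the text does not say so, and the literal reading gives two answers. Some analysis sections are absent from the released text of both documents, and one of them may settle the matter.

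Both situations should be rare. The syringes are open label, medication is dispensed through the central system, and kits and diaries are checked, so 24 weeks on the wrong drug is unlikely. Randomization and first injection are both scheduled for Day 1, which leaves little time to withdraw between them. Undosed subjects would rarely have usable biomarker changes, because SAP 8.2 ties baseline to the first dose, so for them only responder rates are affected. SAP 7.3.1 reports both randomized and dosed numbers, so any loss can be seen.

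Finally, the study is exploratory with no primary or secondary endpoint, and restricting a pharmacodynamic comparison to dosed subjects is a defensible choice. These points limit the size and urgency. They do not remove the ambiguity or the unequal treatment of leavers before and after the first dose.

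**Conclusion.** The point stands as a low-cost improvement. It does not invalidate the planned comparisons.

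On the released text, SAP 6.3 and 7.1 are unreconciled for a subject on the wrong drug throughout the single-blind period. Both documents drop randomized but undosed subjects from responder rates under an open allocation. The disagreement between Protocol 8.2 and the SAP is real on the page but may be a version difference.

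At 40 per arm the expected size is about 1 point per undosed subject and 2 to 3 points per regrouped subject, small beside the SAP's stated half-width of 17 to 21 points. This rests on the assumed 40% response in both arms and on such subjects existing at all.

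**What to change.** In SAP 6.3, and in Protocol 8.2 if that text is still current:

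- Group all efficacy and biomarker outputs by randomized arm at every time point, so that 6.3 and 7.1 agree.
- Keep as-received grouping for safety, exposure and immunogenicity.
- Use all randomized subjects as the denominator of responder rates, with undosed subjects as non-responders. SAP 8.3 says missing efficacy values are not imputed, so it should be aligned with the non-responder rule in 7.1 in the same edit.
- Leave biomarker changes as observed, by randomized arm.
- Report the numbers undosed and the numbers on the wrong drug, by arm.

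SAP 7.7.1 mentions a post-hoc threshold already used for the single-blind analysis, which suggests that analysis may have been run. If so, present the regrouped and all-randomized results as a labelled sensitivity analysis and leave the existing population in place.

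The cost is wording, a population flag and, if needed, one extra set of outputs. No new data are required. Responder rates may fall slightly if any randomized subject was not dosed.
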